1.0 BACKGROUND

Depression is a recurrent and persistent disorder associated with impairment in multiple domains and increased risk for substance use disorders and suicide (e.g., Costello, Erkanli, & Angold, 2006; Reinecke & Curry, 2008). Therefore, finding efficacious treatments for depression in adolescents is critical. Medications can reduce depression in youth, but they also can have undesirable side effects (Vitiello & Swedo 2004). Psychotherapies have been shown to successfully reduce depression in children and adolescents, although the overall effect sizes have been modest (e.g., ES=.34; Weisz, McCarty, & Valeri, 2006). A review of 52 RCTs testing the efficacy of psychotherapies for children and adolescents with depression, found that both Interpersonal Psychotherapy [IPT (ES = .56)] and Cognitive Behavioral Therapy [CBT (ES = .46)] were significantly more beneficial than most control conditions at post-treatment and at follow-up (Zhou et al., 2015). Thus, efficacious treatments for youth depression exist, but there is still room to improve upon these treatments. There remains a critical need to improve upon these therapies to reach even more youths with depression.

One variable hypothesized to affect children's interpersonal relationships is their level of social cognitive development on abilities particularly relevant to social functioning (e.g., social perspective taking). This study will test whether an intervention that aims to increase social cognitive (SC) abilities will improve these skills in youth with depression. We focus on the particular social cognitive abilities of perspective taking/theory of mind (ToM), because impairment in these skills has been associated with greater difficulties in interpersonal relationships and with depression (e.g., Bora & Burk, 2016; Nestor, Sutherland, & [name], 2022). Social perspective taking ability also has a clear link to the skill of cognitive reappraisal, which is taught in CBT ([name] et al., 2016). The Social Cognitive abilities that are the focus of this intervention include recognition that other people may not see things the same way one does, which helps people have a better understanding of others' thoughts and feelings. This is particularly important when a person is experiencing disappointment or anger about what another person did or did not do. By taking the other person's perspective, the aim is for the person to see that their belief about the situation might not be what is going on.

Youths (ages 12-17) with depression diagnoses or clinical levels of depressive symptoms (CDRS-R ≥ 35) will be randomly assigned to either the social cognitive training enhanced CBT (CBT+SCT) or to CBT only. Pre- and post-treatment evaluations will assess social cognitions and depression. If the CBT+SCT intervention significantly improves children's SC abilities and decreases their depressive symptoms, then this will substantially improve clinical care.

2.0 SPECIFIC AIMS

This randomized controlled trial (RCT) aims to treat youths ages 12- to 17-years-old who have a current diagnosis of a depressive disorder or high levels of depressive symptoms (CDRS-R ≥ 35). The aim is to test the effects of CBT+SCT for (1) increasing children's social cognitive (SC) abilities. We also will examine the effects of the treatments on reducing depressive symptoms.

Hypothesis: Adolescents receiving CBT+SCT will show significantly higher levels of SC abilities at post-intervention, controlling for pre-intervention levels, as compared to youth in CBT alone.

Exploratory Hypothesis: Youth in CBT+SCT will show significantly lower levels of depressive symptoms at post-intervention, controlling for baseline levels, as compared to youth in CBT only.

3.0 Inclusion/Exclusion Criteria

Inclusion Criteria

1. Participants ages 12-17 years at the time of enrollment
2. Participants with a current diagnosis of a depressive disorder (Major Depression, Pervasive Depressive Disorder, Depression not otherwise specified) as defined by the Diagnostic and Statistical Manual of mental disorders (DSM-5) or clinical levels of depressive symptoms (CDRS-R ≥ 35).

Exclusion Criteria

1. Serious, current suicidality or in need of more intensive services (e.g., partial or inpatient programs)
2. Current substance or alcohol use disorders
3. A lifetime history of schizophrenia, psychosis, mania, or conduct disorder

4.0 ENROLLMENT/RANDOMIZATION Eligible participants will be randomized to either CBT+SCT or CBT only; randomization will be stratified by teens' age (12-14, 15-17), sex, race/ethnicity, and current medication use.

5.0 Study Procedures

Phone Screen. Study team members will conduct an initial phone screen with parents/guardians to determine initial study eligibility of the child for the study. Participants who appear eligible following the phone screen will be invited to complete a diagnostic interview to verify study eligibility.

Eligible teens will be randomly assigned to one of the two individual treatments with a Masters-level or PhD therapist for up to 12 sessions and they will complete assessments before and after treatment

Treatment appointments will be scheduled at a time that is mutually agreed upon among participants and providers – most likely afternoons or early evenings. Participants taking medications will be able to continue. All appointments may be conducted remotely (i.e., Zoom).

Assessments

- The first assessment is an interview with the parent and teen separately to determine eligibility for the study.
- Interviews take about 2 hours and are recorded via Zoom.
- The second interview will occur at the end of treatment about 12 weeks after the start of treatment.
- Participants will complete online surveys at pre- and post-treatment evaluations (about 60 minutes).
- Teens also will complete measures on the computer administered by a research assistant (60 minutes).

Treatment

- Eligible teens will be assigned randomly to one of the treatments. Both therapies teach skills for coping with stress, problem solving, assertive communication, engaging in positive activities, and realistic thinking. In addition, CBT+SCT teaches additional skills for taking others' perspectives.
- Teens will meet remotely with a therapist for individual sessions (about 50 minutes). Therapy sessions will be recorded via Zoom for quality control (i.e., to ensure that the therapist covers the material correctly).
- Teens will receive up to 12 individual therapy sessions as part of the study. Additional sessions beyond 12 are not considered part of the research protocol, but teens may continue therapy with their original therapist, or we can provide referral information to another therapist if desired.

Compensation for participation

Parents and children will be paid for completing the assessments. Gift cards (e.g., Amazon) will be given after completion of each assessment as follows:

- A parent and teen participant will be paid for completing all parts of the study as follows:
 \$50 for the first assessment (pre-treatment: to determine eligibility)
- If eligible and child participates in the study, then \$50 for the post-treatment assessment
- Payments will be made through gift cards (e.g., Amazon), given after completion of each assessment.

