Data monitoring and participant safety: The DSMB first will review and approve the protocol and subsequently conduct annual reviews to determine whether participant safety has been adequately safeguarded and enrollment goals have been met. The DSMB will be informed of any protocol-related serious adverse events when they occur. The PI will take whatever immediate action is necessary to safeguard the welfare of participants; the DSMB also will be called upon to render judgments if any serious clinical problems (e.g., serious suicidal intent) occur. The DSMB will serve as the final arbiters of whether individual participants should be removed from the study. The DSMB also will be called upon to render judgments when any serious clinical problems (e.g., serious suicidal intent) occur. Psychiatric or other life crises that are high risk and imminent will be acted upon immediately with staff linking participants to appropriate crisis services. These are reviewed immediately with the clinically responsible PI. Lower risk and less imminent crises are reviewed within 48 hours by the clinically responsible PI. Interim analyses will be conducted at each annual review for safety only, not effectiveness. Assuming there are no safety issues, we will prepare the data for analysis.

Critical Incident Protocol & Reporting of Adverse Events: We will collect interview and questionnaire data that could indicate potential harm to participants (e.g., participants expressing intent to harm self or others, or data indicating child, spousal, elder or other forms of abuse or neglect). The *Critical Incident Protocol* will be triggered if a participant reveals information indicating possible or actual harm to themselves or others. Information collected by questionnaires will be monitored by research staff within a day of data collection. All adverse events or unanticipated problems involving risk to participants or others will be reported to the appropriate agency as required including the IRB, specific state agency and stakeholders (TN), the Data Safety and Monitoring Board, and the National Institute of Mental Health. The clinically responsible PIs will monitor and report any adverse events. The PIs also will supervise all study staff, interviewers, and therapists to ensure that all required protocol procedures are followed.

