8.0 Statistical Analysis Plan

We will use the general linear model (i.e., MANCOVA) to test hypotheses. The between subjects factor will be *Condition* with two levels (CBT+SCT vs. CBT only) and the within-subjects factor will be Time with two levels (baseline, post-test). We will adopt a multivariate approach to repeated measures (as assumptions of compound symmetry are untenable). Dependent variables (DVs) will vary across analyses; child age and sex, will be covariates in all analyses.

Specific Aims. To test whether youth in CBT+SCT have better SC skills at post-treatment than youth in CBT only at post-treatment.

Hypothesis: We will test the effect of CBT+SCT on SC skills (target) using the *Faux Pau* task as the DV. We will first test the 2x2 Condition x Time interaction. We expect that a 2x2 partition of this interaction will be significant, reflecting the Condition effect from baseline to post-test.

Exploratory Hypothesis: To test the effect of CBT+SCT on depressive symptoms, the DV will be the clinician-rated depression measure (CDRS). Analyses will be the same as described for the main hypothesis except that we will test the depression measure as the dependent variable.

Power. To estimate power, we assumed that autocorrelations among the repeated measures were .4 - .6. With N=42 (21 per cell), alpha = .05, and a medium effect size (e.g., a .40 SD Condition effect at T2), we will have approximately .82 power to detect the initial 2x2 Condition x Time interaction ($f_v = .32$). Assuming correlations of .3-.6 among the same measure over time, alpha = .05, and medium effect sizes we will have .85 power for the 2x2 Condition by Time interaction.

9.0 Privacy/Confidentiality Issues: Methods for protecting privacy and confidentiality.

All research data will be coded with a study ID number rather than names. No identifying information will be stored with research data. A database linking participant contact information to study ID numbers will be password-protected and stored on a secure server. Only key study personnel involved in contacting participants will have access to this information. Questionnaire data will be collected and stored online.

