STUDY TITLE: Mind over Mood

R61 PHASE: Social Cognitive Training to Enhance the Efficacy of CBT for Depression in Youth:
A Developmental Approach

STUDY IRB NUMBER # 190077

PRINCIPAL INVESTIGATOR

[name]., Vanderbilt University, Department of Psychology and Human Development

SPONSOR NAME

National Institutes of Health (NIH)
NIH Grant/Sponsor # R61 MH115125

VERSION DATE: SAP adapted from the IRB Application approved on 06/02/2019

ClinicalTrials.gov Identifier: NCT03954392

Statistical Analysis Plan

We will use the general linear model (i.e., MANCOVA) to test hypotheses. The between subjects factor will be *Condition* with two levels (CBT+SCT vs. CBT only) and the within-subjects factor will be Time with two levels (baseline, post-test). We will adopt a multivariate approach to repeated measures (as assumptions of compound symmetry are untenable). Dependent variables (DVs) will vary across analyses; child age and sex, will be covariates in all analyses.

Specific Aims. To test whether youth in CBT+SCT have better SC skills at post-treatment than youth in CBT only at post-treatment.

Hypothesis: We will test the effect of CBT+SCT on SC skills (target) using the *Faux Pau* task as the DV. We will first test the 2x2 Condition x Time interaction. We expect that a 2x2 partition of this interaction will be significant, reflecting the Condition effect from baseline to post-test.

Exploratory Hypothesis: To test the effect of CBT+SCT on depressive symptoms, the DV will be the

clinician-rated depression measure (CDRS). Analyses will be the same as described for the main hypothesis except that we will test the depression measure as the dependent variable.

Power. To estimate power, we assumed that autocorrelations among the repeated measures were .4 - .6. With N=42 (21 per cell), alpha = .05, and a medium effect size (e.g., a .40 SD Condition effect at T2), we will have approximately .82 power to detect the initial 2x2 Condition x Time interaction ($f_v = .32$). Assuming correlations of .3-.6 among the same measure over time, alpha = .05, and medium effect sizes we will have .85 power for the 2x2 Condition by Time interaction.

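### Does leaving therapist out of the model make the Condition test too liberal?

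*Protocol*

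**What the plan says.** Protocol section 5.0 has each teen treated individually: "Eligible teens will be randomly assigned to one of the two individual treatments with a Masters-level or PhD therapist for up to 12 sessions". The treatment bullets in that section add that, after the study sessions end, "teens may continue therapy with their original therapist". This suggests that a teen stays with one therapist throughout. Section 6.0 confirms that there is more than one therapist: "The PIs also will supervise all study staff, interviewers, and therapists".

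Therapist is not a randomization stratum. Section 4.0 stratifies by age band, "sex, race/ethnicity, and current medication use". Nor is it a model term. Protocol section 8.0 states "We will use the general linear model (i.e., MANCOVA) to test hypotheses". The SAP repeats the same model: "The between subjects factor will be *Condition* with two levels (CBT+SCT vs. CBT only", with Time as the within-subjects factor, and "child age and sex, will be covariates in all analyses". Neither document gives the number of therapists, their caseloads, how teens are allocated to them, or whether a therapist delivers one arm or both.

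**The concern.** Teens who share a therapist may have correlated outcomes. If each therapist delivers only one arm, a stronger therapist in one arm looks the same as a benefit of the added social cognitive training, and randomizing teens does not remove that. The model would count 42 independent teens when the information on Condition comes from a few therapists. The standard error would be too small and the .05 level would be exceeded. The stated mix of Masters-level and PhD staff makes some therapist differences plausible. The Condition by Time test on the social cognition task carries the trial's only non-exploratory hypothesis, so a false positive there would matter.

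**Working it through.** **Inputs from the documents.** There are 21 teens per arm and alpha is .05 (section 8.0 and SAP). With two time points, the Condition by Time test is the arm difference in change score.

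**Assumed inputs, because the documents give none.** Therapists per arm k = 2 to 7; therapist ICC on the analysed score .01 to .10.

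**The plan's own figure.** The figure at issue is the .05 level. With ICC = 0, simulated type I error is .048 to .051, so the planned test is sound when teens are independent. The stated power of .82 is a separate matter and is not used here.

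**Arm-specific therapists.** Let m be the size-weighted caseload.

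- Design effect = 1 + (m − 1) × ICC
- Approximate type I error = 2 × [1 − Φ(1.96/√design effect)]

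Example with k = 3 and ICC = .05:

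- m = 21/3 = 7
- Design effect = 1 + 6 × .05 = 1.30
- Model SE / true SE = 1/√1.30 = .877
- Effective N = 42/1.30 ≈ 32
- Approximate type I error = .086 (simulated .085)

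Simulated type I error, 40,000 runs:

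| Therapists per arm | ICC .01 | ICC .02 | ICC .05 | ICC .10 |
|---|---|---|---|---|
| 2 | .063 | .075 | .107 | .165 |
| 3 | .057 | .063 | .085 | .125 |
| 4 | .055 | .060 | .076 | .102 |
| 5 | .054 | .058 | .070 | .092 |
| 7 | .052 | .055 | .062 | .073 |

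A change-score model with age and sex, with the therapist effect on the post-test score and a pre-post correlation of .5, gives .104, .086 and .079 for 2, 3 and 4 per arm at ICC .05. Adjusting for baseline instead gives .124, .099 and .088. The residual variance is then 1 − .5² = .75, so the therapist share rises to .05/.75 = .067.

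**Therapists delivering both arms.**

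- Arms balanced within therapist, constant treatment effect: .042 to .050.
- Teens assigned without regard to arm, constant treatment effect: .049 to .051.
- Not balanced, and the treatment effect varies by therapist (variance .05 to .10): .057 to .090.

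**What a therapist-level analysis would cost.** If therapists are nested in arm, comparing therapist means leaves 2(k − 1) degrees of freedom: 4, 6 and 12 for k = 3, 4 and 7. At ICC .05:

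| Therapists per arm | CI width relative to planned test | Power at .9 SD, means / planned | Power at .40 SD, means / planned |
|---|---|---|---|
| 3 | 1.49 | .50 / .79 | .14 / .28 |
| 4 | 1.30 | .60 / .80 | .17 / .27 |
| 7 | 1.12 | .72 / .80 | .21 / .26 |

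A random therapist intercept does not rescue this. Its variance is estimated as zero in 31 to 42% of runs at ICC .05 to .10, and its type I error ranges from .007 to .050.

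**A rule that significance must survive adjustment.** Take a real treatment effect and no therapist effect at all. Among significant planned tests, the therapist-mean test then fails in 30%, 19% and 9% (k = 3, 4, 7) at .9 SD, and in about 48%, 38% and 22% at .40 SD. Those true effects would be labelled inseparable from therapist differences only because degrees of freedom were lost.

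**The case for a change.** The strongest case for a change is that the facts are not in dispute and the remedy is cheap. Recording a therapist identifier and naming one adjusted analysis costs a data field and a paragraph. Fixing it in advance would stop the adjustment from being chosen or dropped once results are known. The same model also serves the depression outcome.

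Part of this stands. A reader cannot tell which arrangement applies. With 2 or 3 arm-specific therapists per arm and an ICC of .10, the error rate would be .165 or .125, which is not trivial.

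It does not carry the point further, for three reasons.

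- The harm needs arm-specific delivery, few therapists and a material ICC together, and the documents support none of these. Section 5.0 has a research assistant administer the teens' computer measures. If the social cognition task is among them, as seems likely, the therapist does not administer it. Therapists could still affect learning, but nothing favours an ICC of .05 to .10 over .01 to .02.
- An adjusted estimate placed beside the planned test would be imprecise and would decide nothing. If therapists are shared, a check for treatment effects that vary by therapist detects a variance of .05 to .10 in only 6 to 10% of runs with 3 or 7 therapists.
- Adding therapist as a stratum is not practical. Even if race/ethnicity and medication each had two levels, the present factors make 2 × 2 × 2 × 2 = 16 cells, or 42/16 ≈ 2.6 teens per cell.

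**Conclusion.** The omission is real, but it does not make the planned test wrong on what the documents show. Under assumed arm-specific delivery with 3 to 7 therapists per arm, type I error is about .05 to .065 at ICC .01 to .02 and .06 to .12 at ICC .05 to .10. It is higher with 2 per arm. If therapists are shared and the treatment effect is constant, it is .042 to .051.

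Keeping the teen-level test in a 42-person trial is a fair trade-off. The alternative gives up .08 to .29 of power at .9 SD (.80 − .72 with 7 per arm; .79 − .50 with 3), and using it as a gate would reject real effects.

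What remains is missing description of the number of therapists, their caseloads and whether each worked in one arm or both. A trial report ordinarily supplies this, and analysts can show a therapist-adjusted estimate with its confidence interval without altering the prespecified test. If therapists prove to have been few and arm-specific, a significant result should be read with the table above in mind. No change to the plan follows.

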Adverse events and clinical worsening of symptoms. Because the intervention sessions address sensitive issues for participants and are designed to help youth modify their cognitions, there may be a temporary increase in anxiety or other negative emotions. Therapists will monitor youth for such adverse reactions. If significant problems are identified, then the therapist will discuss the case with Drs. [name] or [name] to determine if further intervention is needed. We will follow the guidelines defining adverse events, serious adverse events, and unanticipated problems set forth by the IRB at Vanderbilt University. All serious adverse events will be reported to the IRB according to the procedures outlined in their regulations. We will monitor participants' depressive symptoms at the pre- and post-intervention. We also have participants complete the PHQ each week to check for individuals whose symptoms may have worsened requiring further evaluation and clinical service. If a participant reveals currently active suicidal ideation, attempts, or non-suicidal self-injury during therapy or the clinical evaluation, therapists and evaluators will follow the "critical incident" plan that specifies what should be done if such an event occurs. Therapists and evaluators will have information about how to contact clinical supervisors (PIs) if they have any questions about what to do at any point. All such serious incidents are reported within 48 hours to the Vanderbilt IRB and DSMB.

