7.0 Study Withdrawal/Discontinuation

The PI may recommend that a participant be taken out of the research study to ensure his/her safety and well-being. Some reasons include:

- If the PI or therapist determines that a participant is not receiving the appropriate treatment
- The participant's condition worsens, reports serious suicidality, or is deemed to be a risk to

him/herself or others. A participant may require more intensive treatment. In either case, the research team will discuss this with participants and will provide them with other appropriate clinical resources, as needed.

If a participant wants to withdraw from study participation, they should tell the therapist, interviewer, or Project Coordinator. Deciding not to be part of the study will not affect their medical care in any way.

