- Participants' de-identified, coded research information may be put in one or more databases and used for future research. Information stored in these databases will not include any identifying information such as participants' name, address, telephone number, or date of birth. Participants' research data will only be available to researchers who have received approval from data access committees and/or Institutional Review Boards. Some of these databases are maintained by Vanderbilt, some are maintained by the federal government, and some are maintained by other institutions.
- If any publication or presentation results from the research, no personally identifiable information will be shared. Participants' de-identified research data will be maintained indefinitely to verify the integrity of the data and validity of results.

Privacy: All efforts, within reason, will be made to keep participants' information private. Using or sharing ("disclosure") such data must follow *federal privacy rules*. By signing the consent for this research study, participants are agreeing ("authorization") to these uses and sharing of data.

Vanderbilt University may share the results of the study to the following groups: the Federal Government Office for Human Research Protections, the Vanderbilt University Institutional Review Board, or the study sponsor (National Institute of Health). Federal privacy rules may not apply to these groups; they have their own rules and codes to assure that all efforts, within reason, will be made to keep participants' research data private. Participants' data will be shared with the appropriate authority as required by law if someone is in danger of being harmed, or a participant has experienced physical or sexual abuse or neglect.

The study results will be kept in participants' research record for at least seven years after analyses of the study data are finished. Unless told otherwise, participants' consent to use or share de-identified data does not expire. If participants change their mind, they should contact [name] in writing and let her know that they withdraw their consent. Her mailing address is Department of Psychology & Human Development, [name]. At that time, we will stop getting any more data from the participants, but the data we stored before withdrawal of consent may still be used for reporting and research quality.

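### The plan does not say when the only post-test is due if therapy ends well away from week 12, or that teens removed from the study are still assessed.

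*Protocol*

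**What the plan says.** **Timing.** Protocol section 5.0 plans one assessment before and one after treatment. The timing rule for the second is: "The second interview will occur at the end of treatment about 12 weeks after the start of treatment". The surveys are placed at pre- and post-treatment, and the computer-based measures carry no timing of their own.

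**Length of treatment.** Section 5.0 sets a maximum: "Teens will receive up to 12 individual therapy sessions as part of the study". It gives no minimum number of sessions, no session frequency and no definition of completion. Therapy may also run on outside the study: "Additional sessions beyond 12 are not considered part of the research protocol, but teens may continue therapy with their original therapist".

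**Removal.** Section 7.0 states: "The PI may recommend that a participant be taken out of the research study to ensure his/her safety and well-being". One listed reason begins: "The participant's condition worsens, reports serious suicidality, or is deemed to be a risk to". Section 6.0 makes the DSMB the final arbiter of individual removals. Neither section says whether a removed teen still has the post-test. Section 9.0 ends data collection when a participant withdraws consent in writing: "At that time, we will stop getting any more data from the participants".

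**Analysis.** Section 8.0 and the SAP use a MANCOVA with Condition (two levels) and Time (two levels: baseline and post-test), adjusted for age and sex. Neither states an analysis population or a rule for missing post-tests.

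**The concern.** Both hypotheses rest on a single post-baseline measurement, so its timing and completeness carry the whole comparison.

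The first gap is timing. The two anchors name the same date only if treatment ends near week 12. If it does not, two members of staff could follow the protocol faithfully and assess the same teen on different dates. For example, if sessions were weekly (an assumption) and a teen stopped after the fourth, the two dates would be about 12 − 4 = 8 weeks apart. The analysis treats all post-tests as one time point.

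The second gap is completeness, and it is the more serious one because it follows from a stated rule. Removal is from the research study, not only from therapy, and worsening is a listed reason. If removal ends assessment, the teens who are lost are partly chosen by how they were doing. The CDRS is exposed most directly. For the Faux Pas task, the outcome of the main hypothesis, the link depends on how social cognitive skill relates to clinical course, which the documents do not describe.

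**Working it through.** **1. What follows from the text**

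| Situation | Which post-test date applies? | Is the post-test still collected? |
|---|---|---|
| Treatment ends near week 12 | Both anchors agree | Yes |
| Therapy stops well before week 12, teen stays in study | Not stated | Not excluded, but no explicit rule |
| Sessions run well past week 12 | Not stated | Yes |
| Teen taken out of the research study | Not stated | Not stated |
| Consent withdrawn | None | No (section 9.0) |

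**2. The plan's own power figure**

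Inputs from section 8.0 and the SAP: N = 42 (21 per cell), alpha .05, f_v = .32, stated power about .82. With a noncentral F on 1 and 40 degrees of freedom and two time points:

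- λ = f_v² × 2N = .1024 × 84 = 8.60, power .816.
- Equivalent form: λ = f² × N × 2 / (1 − ρ) with f = .25 and ρ = .4 gives .0625 × 84 / .6 = 8.75, power .823. Here f_v = .25/√.6 = .323.

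The stated .82 is reproduced. It presumes that all 42 teens have both measurements.

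**3. Power when post-tests are missing**

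The same formula with N − 2 denominator degrees of freedom. The numbers missing are assumptions, because the documents give no rate.

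| Post-tests missing | N analysed | λ | Power |
|---|---|---|---|
| 0 | 42 | 8.75 | .82 |
| 4 | 38 | 7.92 | .78 |
| 8 | 34 | 7.08 | .73 |
| 12 | 30 | 6.25 | .68 |

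These rows use f = .25, which corresponds to about a 1.0 SD difference at post-test with equal baselines, not to the .40 SD that the plan also quotes. With .40 SD analysed as change and ρ = .4 to .6, power is .21 to .29 at N = 42 and .16 to .22 at N = 30. That mismatch is a separate matter. Missing post-tests cost power on either basis.

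**4. Bias from off-time assessment**

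Bias = (arm difference in the share of teens assessed off-time) × (outcome shift from being off-time, in SD). The documents give neither factor. Illustrative ranges:

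- Low: .05 × .1 = .005 SD.
- High: .20 × .3 = .06 SD.
- Equal shares and equal shifts in both arms: 0.

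**5. Bias from outcome-related loss**

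Suppose k of 21 teens in one arm have no post-test, each would have scored 1 SD worse than that arm's mean, and the other arm loses none. The observed mean of the affected arm then moves by k/(21 − k):

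- k = 1: 1/20 = .05 SD.
- k = 2: 2/19 = .11 SD.
- k = 3: 3/18 = .17 SD.

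The shift makes the affected arm look better than it was. It cancels from the arm difference if both arms lose the same number of similar teens. Both k and the 1 SD are assumptions, so this shows how sensitive 21 per cell is and does not estimate what will happen.

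**The case against.** The strongest reply is that the timing sentence describes one visit in two ways, and that staff would in practice apply the 12-week mark to everyone. Section 5.0 says that randomised teens complete assessments before and after treatment, the post-test payment has no session minimum, and data collection is expressly ended only on withdrawal of consent. The rule and the 12-session cap are the same in both arms.

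Much of this stands. A reader might infer that every teen who does not attend 12 weekly sessions is assessed at the wrong time or not at all. The documents do not say that. No weekly schedule for sessions is stated, 12 is a maximum, and the wording of the time point allows slack, so a teen with fewer sessions ending near week 12 meets both anchors. For a teen who only stops therapy, the text is silent, and either anchor could be applied consistently. The scheduling sentence, "Treatment appointments will be scheduled at a time that is mutually agreed upon among participants and providers", goes on to mention times of day and says nothing about frequency. The nearest hint of rhythm is a safety check, "We also have participants complete the PHQ each week to check for individuals whose symptoms may have worsened", and it points to regular contact.

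A reader might also infer that the extra content in CBT+SCT shifts assessment times or dropout between arms. That is possible, but nothing in the documents shows it.

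The reply does not cover removal. Sections 6.0 and 7.0 provide for it without saying that assessment continues, and the analysis has no stated way to handle a teen without a post-test. The weekly PHQ is not a study outcome and is not offered as a substitute.

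**Conclusion.** The concern holds in limited form. The protocol leaves open which anchor governs the only post-test when treatment ends well away from week 12, and it allows removal for worsening without providing for the post-test to be collected. With a two-time-point MANCOVA, which ordinarily uses only teens with both measurements, this can produce outcome-related loss and reduced power.

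The documents do not allow the size of the bias, its direction between arms, or the number of teens affected to be computed. The figures above are illustrations: power of .82 falling to .68 if 12 of 42 post-tests are missing, timing bias of 0 to .06 SD, and a shift in one arm's mean of .05 to .17 SD for one to three selectively lost teens. They rest on the stated assumptions about missing numbers, arm differences and outcome shifts. A claim that the planned effect is biased by a particular percentage would go beyond the documents. This is a cheap improvement worth making, not evidence that the comparison is invalid.

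**What to change.** 1. **Protocol section 7.0:** distinguish stopping study therapy from leaving study assessments, and state that the first does not imply the second.
2. **Protocol section 5.0:** replace the double anchor with one rule, for example: the post-treatment assessment (interview, surveys and computer measures) is sought from every randomised teen at about 12 weeks after the start of treatment, within a stated window, whatever the number of sessions attended and whether or not study therapy has stopped, unless consent to assessment is withdrawn. The investigators should choose the window and keep it as narrow as scheduling permits.
3. **Data collection:** record the actual assessment date and the number of sessions attended.
4. **Section 8.0 and SAP:** state that all randomised teens with a post-test are analysed in their assigned arm, and report missing post-tests by arm with reasons.

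This changes measurement only. Who stops therapy, who is referred and how a teen is cared for stay as they are. The post-test and its $50 payment are already planned, and appointments may be held remotely, so the cost is wording plus some extra scheduling and tracing. One real downside is that a teen whose sessions run late may be assessed before the last one, which departs slightly from a strict post-intervention measurement. The recorded dates and session counts would show how often that happens.
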